7.5 Follow-up of AEs and SAEs

All AEs, regardless of seriousness, must be followed until resolution, until the condition stabilizes, until the event is otherwise explained, or the subject is lost to follow-up. The investigator is responsible to ensure that follow-up includes any supplemental investigations as may be indicated to elucidate as completely as practical the nature and/or causality of the AE. This may include additional laboratory tests or investigations, histopathological examinations, relevant hospital records (i.e. discharge summary), or consultation with other health care professionals.

Salix may request that the investigator perform or arrange for the conduct of supplemental measurements and/or evaluations. If a subject dies during participation in the study or during a recognized follow-up period, Salix should be provided with a copy of any postmortem findings, including histopathology.

For SAEs, new or updated information should be recorded on the originally completed paper SAE Report Form and all changes signed and dated by the Investigator or designee. By signing the SAE Report Form, the investigator or designee attests to the accuracy and completeness of the data and that he/she has reviewed and approved the report being submitted. The investigational sites IRB/IEC must be notified about SAEs in accordance with the requirements of the governing IRB/IEC.

7.6 Prompt Reporting of SAEs to Salix Pharmaceuticals

SAEs must be reported promptly to Salix Product Safety or Designee once the investigator determines that the event meets the protocol definition of a SAE.

Prompt reporting of a SAE requires:

- Completion and transmission of the SAE Report Form to Salix Product Safety or Designee
 via fax within 24 hours of the investigator's knowledge of the event. In parallel, a
 corresponding AE with the SAE details should be entered into the AE CRF.
- Prompt reporting of additional information for previously reported SAEs should follow the same reporting timeframe as initial reports. In addition, the corresponding AE in the AE CRF (as applicable) should be updated to ensure all data points documented in the AE CRF are aligned with the matching data points on the paper SAE Report Form.

7.7 Pregnancy Reporting

Pregnancies detected in subjects assigned to study treatment should be promptly reported to Salix Product Safety or Designee via fax as soon as the investigator is notified using the Salix Pregnancy Notification Form. If a female subject becomes pregnant following assignment to study treatment, the study product will be immediately discontinued and the subject will be

followed until the outcome of the pregnancy is known. (Refer to the 'Females of Reproductive Potential' Section 4.4).

Salix Product Safety or Designee should be notified via fax of any updates on the status of the pregnancy as soon as the information becomes available by update and/or amendment of the initial pregnancy notification form.

Although pregnancy occurring in a clinical study is not considered to be an AE or SAE, any pregnancy complication or elective termination of a pregnancy, for medical reasons, will be recorded as an AE or SAE and followed as such.

7.8 Transmission of SAE Report Forms and Pregnancy Notification Forms

Completed SAE Report Forms and completed Pregnancy Notification Forms should be transmitted via the country specific fax numbers listed in the SAE Form Completion Guidelines which are provided in the Study Reference Manual.

For questions regarding SAE and/or Pregnancy reports, country specific phone numbers are listed in the SAE Form Completion Guidelines which are provided in the Study Reference Manual.

7.9 Regulatory Reporting Requirements for SAEs

The investigator, or responsible person per local requirements, must comply with the applicable local regulatory requirements related to the reporting of SAEs and expedited safety reports to regulatory authorities and their IRB/IEC.

Confidential

8.0 STATISTICAL CONSIDERATIONS

A detailed statistical analysis plan will be prepared for this study. The plan will contain a discussion of the statistical methods, a description of the computational algorithms and data handling conventions, and specifications for the data summaries and listings. It will be finalized before database lock.

8.1 Randomization

Subjects who successfully complete the Screening Period will enter the Treatment Period and will be randomized in a 1:1 allocation to one of two treatment groups for the duration of the study as assigned by the means of centralized electronic randomization system.

Randomization will be stratified by study center within a country. Treatment groups are as follows:

Treatment A: Rifaximin DR 800 mg BID

Treatment B: Placebo BID

8.2 Determination of Sample Size

The information below provides the background information for sample size determination for the induction of clinical remission with endoscopic response at 16 weeks followed by clinical and endoscopic remission at 52 weeks. For placebo, the expected rates are based on data from a Phase 2 study (RETIC 03/06) conducted in subjects with active moderate Crohn's disease. The rates for Rifaximin DR are based on the assumption that Rifaximin DR will provide a somewhat higher induction of remission rate.

Expected rates for induction of clinical remission with endoscopic response at Week 16 are 40% for placebo and 55% for Rifaximin DR.

Based on a significance level of 5% (alpha 0.05), a sample size of approximately 240 subjects per treatment group will have at least 90% power to test the hypothesis that Rifaximin DR is superior to placebo for each co-primary endpoint considered individually. Approximately 80% power is available to detect significant differences between Rifaximin DR and placebo for both co-primary endpoints.

For the Long Term Treatment Phase, a 15% treatment effect is expected for both clinical symptom and endoscopic remission at Week 52. Based on this assumption and testing at a significance level of 5% (alpha 0.05), a sample size of approximately 210 subjects per treatment group will have at least 90% power to test the key secondary efficacy hypothesis that Rifaximin DR is superior to placebo when each key co-secondary endpoint is considered individually. In addition, approximately 80% power is available to detect significant differences between Rifaximin DR and placebo for each of the key co-secondary endpoints.

An additional consideration for sample size determination is the application of an inflation factor of 20% to account for drop-out rates during the Induction and Long Term Treatment Phases of the study. This consideration suggested that 330 subjects per treatment group would be required at study entry.

8.3 Analysis Populations

Intent-to-Treat (ITT) Population

The ITT population will include all randomized subjects who take at least one dose of study drug.

Per Protocol (PP) Population will include all subjects in the ITT Population with the exception of those who failed to meet Inclusion Criteria 3 and 4; or met Exclusion Criteria 1, 2, 13 or 14.

The analyses of baseline characteristics and efficacy will be performed for the ITT Population. The primary efficacy analysis also will be performed on the PP Population as a sensitivity analysis. All safety analyses will be performed on the ITT Population.

8.4 Subject Disposition

Subject disposition will be summarized by treatment and study phase and will include the number of subjects entered in the study; number and percentage of subjects who completed or prematurely discontinued (classified by reasons for premature discontinuation); the number of subjects entered in the study at each study site; and the number and percentage of subjects who completed or discontinued at each study site.

8.5 Demographic and Baseline Characteristics

Demographic and baseline characteristics will be summarized descriptively by treatment group. Baseline will be defined as the last assessments prior to initiating the Treatment Period. The following demographic and baseline disease characteristics will be summarized:

Demographics:

- Age (years) = (date of informed consent signed date of birth)/365.25;
- Age group (<65, >=65);
- Sex (male/female);
- Ethnicity (Hispanic or Latino/not Hispanic or Latino);
- Race (American Indian or Alaskan Native, Asian, Black or African-American, Native Hawaiian or Other Pacific Islander, White, and Other); subjects who identify more than one race will be categorized as "Other";

Confidential

- Height (cm);
- Weight (kg);
- Body mass index (kg/m2) = (Weight in kg)/ (Height in m)2;
- Region (US/Rest Of World).

Baseline characteristics:

All baseline subject characteristics including demographic data (outlined above), baseline CDAI and SES-CD scores, duration of the disease (years), location of disease, previous steroid use (dose, duration), previous surgery for CD, smoking history (nonsmoker/exsmoker/smoker), baseline CRP and fecal calprotectin values will be summarized by treatment arm. Baseline comparability will be assessed via descriptive measures, e.g., by comparing means, 95% confidence intervals and proportions.

8.6 Analysis Methods

The phrases 'statistical analysis' or 'analysis' will be used to mean inferential analysis (such as performing tests of significance, reporting p-values and confidence intervals). When no inferential analysis will be performed, the phrases 'descriptive analysis' or 'descriptive statistics' will be used (for instance, producing summary tables of means, standard deviations, percentages of responders). All efficacy analyses will be conducted on ITT and PP populations. All efficacy analyses will adjust for country.

8.6.1 Primary Efficacy Analysis

Induction Phase

There will be two co-primary measures of efficacy assessed during the Induction Phase. The first co-primary endpoint is:

 Clinical symptom remission defined by (1) the total number of liquid/very soft stools for the 7 days prior to the Week 16 visit being ≤ 10 (from CDAI Item 1); AND (2) an abdominal pain rating of ≤ 1(from CDAI Item 2) on each day for the 7 days prior to the Week 16 visit.

The second co-primary endpoint is:

 Endoscopic response defined as a ≥3-point decrease in the SES-CD from baseline to the SES-CD score obtained between Week 16 and Week 17. SES-CD scores will be calculated from centrally-read digital video of ileocolonoscopies performed at baseline and between Week 16 and Week 17.

For each endpoint, the null hypothesis H0: πR - πP =0 versus the alternative HA: πR - $\pi P \neq 0$ is of interest, where πR is the binomial parameter for induction of remission/response for the

Rifaximin DR group, and πP is the binomial parameter for induction of remission/response for the placebo group. Subjects who require the initiation of rescue medication and/or surgery for CD will be considered treatment failures from the date of the introduction of the rescue medication and/or surgery, regardless of their actual response data. The Cochran-Mantel-Haenszel (CMH) test, stratified by country, will be used to test the hypothesis. Each null hypothesis of no difference will be rejected if the resulting p-value for the respective statistical test is less than 0.05. Significance for the induction claim will only be declared if both null hypotheses are rejected. As such, the overall Type I error rate will be maintained at the 5% level without adjustment for multiple comparisons.

If it is evident that the response variable is confounded with some of the background variables, then logistic regression will be performed using the background variables as covariates. The differences between this adjusted analysis and the previous unadjusted analysis will be noted, and the impact of such differences will be discussed.

The primary efficacy analysis will be repeated on the PP population to assess the robustness of the results of the primary outcome.

Long Term Treatment Phase

There will be two key co-secondary endpoints of efficacy assessed during the Long Term Treatment Phase. The first is:

 Clinical symptom remission defined by (1) the total number of liquid/very soft stools for the 7 days prior to the Week 52 visit being ≤ 10 (from CDAI Item 1); AND (2) an abdominal pain rating of ≤ 1 (from CDAI Item 2) on each day for the 7 days prior to the Week 52 visit.

The second is:

 Endoscopic remission defined as a SES-CD score of ≤ 2 at Week 52. SES-CD scores will be calculated from centrally-read digital video of ileocolonoscopies performed at Week 52.

For each endpoint, the number and proportion of subjects with clinical and endoscopic remission will be summarized by treatment group for the ITT Population.

For each endpoint, the null hypothesis H0: $\pi R - \pi P = 0$ versus the alternative HA: $\pi R - \pi P \neq 0$ is of interest, where πR is the binomial parameter for remission for the Rifaximin DR group, and πP is the binomial parameter for remission for the placebo group. Subjects who require the initiation of rescue medication and/or surgery for CD will be considered treatment failures from the date of the introduction of the rescue medication and/or surgery, regardless of their actual response data. The Cochran-Mantel-Haenszel (CMH) test, stratified by country, will be used to test the hypothesis. Each null hypothesis of no difference will be rejected if the resulting p-value for the respective statistical test is less than 0.05. Significance for clinical

and endoscopic remission will only be declared if both null hypotheses are rejected. As such, the overall Type I error rate will be maintained at the 5% level without adjustment for multiple comparisons.

If it is evident that the response variable is confounded with some of the background variables, then logistic regression will be performed using the background variables as covariates. The differences between this adjusted analysis and the previous unadjusted analysis will be noted, and the impact of such differences will be discussed.

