4.3.2 Prohibited Therapy

Use of the following medications is prohibited within the inclusion/exclusion specified prestudy time-frames and throughout the study unless otherwise noted:

- Corticosteroids: Parenteral and rectal steroids are prohibited from the screening visit through the end of the study.
- Any oral or intravenous antibiotic. NOTE: A short course of antibiotic to treat acute conditions (e.g., sinusitis, urinary tract infection) is permitted.
- Use of any drug from the rifamycin class at any time during study participation, including rifaximin, rifampin, rifapentine, and rifabutin. Current international trade names of rifaximin include: Alfa Normix, Colidimin, Faxinorm, Flonorm, Lormyx, Normix, Refero, Rifacol, Rifax-Aw, Rifaxan-Aw, Spiraxin, Targaxan, Tixtar, Tixteller, Xifaxan, Xifaxanta, and Zaxine.
- Any biologicals (e.g., TNFα inhibitor, natalizumab, or similar drugs)
- Cyclosporine, tacrolimus, sirolimus, mycophenolate mofetil, or similar drugs
- Rectal administration of 5-ASA or corticosteroid enemas/foams/suppositories.
- Use of tube or enteral feeding, elemental diet, or parenteral alimentation.
- Introduction of any new probiotics or similar supplements during the study.
- The introduction of any new medication for the treatment of Crohn's disease is prohibited, unless the medication is required in the Investigator's opinion as rescue medication.
 Subjects receiving rescue medication will be considered treatment failures but should remain in the study.

All concomitant medications, including those taken 30 days prior to screening visit, will be documented (drug name, start and stop dates, and indication) in the concomitant medication section of the CRF.

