4.5 Premature Subject Discontinuation

Subjects will be encouraged to complete the study; however, they may voluntarily withdraw at any time. Subjects withdrawn from the study will not be replaced.

A subject may be discontinued from study drug treatment and/or the study for the following reasons:

- Occurrence of an AE and/or SAE, which suggests an unacceptable risk to the subject, in the judgment of the investigator, including worsening of the disease under study.
- Pregnancy (see Section 7.7 for further details).
- Subject request to withdraw.
- Sponsor decision to terminate the study.

For all cases of premature withdrawal from the study listed above or any other, the investigator must provide the reason for discontinuation on the appropriate CRF page. **The** investigator should make every attempt to obtain End of Treatment and End of Study assessments, including ileocolonoscopy.

If treatment with investigational study drug has been prematurely discontinued, the End of Treatment assessments will be completed, and an attempt should be made to have the subject followed for 14 days after last administration of study drug to perform the End of Study assessments.

If a subject prematurely discontinues treatment with investigational drug at any time due to an AE or SAE, the End of Treatment assessments will be completed, and an attempt should be made to have the subject followed at least 14 days to perform the End of Study assessments, or until resolution or stabilization of the condition resulting in withdrawal has been confirmed.

[figure not shown]
The Investigator may discontinue individual subjects from the study at any time during the study. The investigator must provide the reason for discontinuation on the appropriate CRF page.

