7.1 Operating Definitions for Assessing Safety

7.1.1 Adverse Event

An AE is any untoward medical occurrence in a subject or clinical investigation subject administered a study product and which does not necessarily have a causal relationship with the treatment.

An AE can therefore be any unfavorable and unintended sign (that could include a clinically significant abnormal laboratory finding), symptom, or disease temporally associated with the use of a study product, without any judgment about causality (i.e., whether or not considered related to the study product).

An AE does include the following:

- Exacerbation or worsening of a pre-existing illness. NOTE: if the pre-existing illness is
 the disease under study, then "exacerbation" refers to an unexpected worsening from the
 condition at baseline.
- Increase in frequency or intensity of a pre-existing episodic event or condition.
- Condition detected or diagnosed after study product administration even though it may
 have been present prior to the start of the study.
- Symptom associated with disease not previously reported by the subject.

An AE does not include the following:

- Medical or surgical procedures (e.g., surgery, endoscopy, tooth extraction, transfusion) as
 event terms; the condition that led to the procedure is the AE if it meets the definition of an
 AE.
- Situations where an untoward medical occurrence has not occurred (e.g., hospitalization for cosmetic elective surgery, and social and/or convenience admissions).
- Overdose of either study product or concurrent medication without any signs or symptoms.
- Symptoms associated with disease, which are consistent with the subject's usual clinical course; unless the subject experiences worsening of their symptom(s) or the symptom(s) meet the criteria for an SAE.

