8.7.2 Handling of Dropouts or Missing Data

Missing data will be handled using the Worst Case analysis method for the primary and key secondary endpoints. In the Worst Case analysis, subjects with fewer than 4 days of diary data in a given week will be considered non-responders for that week. Additionally, subjects with missing SES-CD data will be classified non-responder for that measure in that week.

The following three sensitivity analyses will be conducted to address the impact of missing data on the primary and key secondary endpoints:

Last Observation Carried Forward (LOCF) Analysis: In the first analysis, missing values will be replaced with the last previous non-missing value. The baseline values will not be carried forward.

Multiple Imputation Analysis: In the second analysis, missing values will be filled in by the multiple imputation method which involves the following distinct phases:

- The missing data will be filled in to generate complete data sets using SAS/STAT procedure PROC MI;
- The complete data sets will be analyzed using PROC LOGISTIC in SAS/STAT;
- The above two steps will be repeated 5 times;
- The results from the complete data sets will be combined for statistical inferenceusing SAS/STAT procedure PROC MIANALYZE.

Observed Case Analysis: In the third analysis, subjects are excluded from the analysis if the subject has insufficient data to be determined as a responder or non-responder in a given 4-week assessment period. This analysis is not based on the ITT population and, therefore, interpretation of results from this analysis requires substantial caution. This is because the subjects who responded in the respective treatment groups may have different distributions for background characteristics. Thus, additional analysis may be undertaken by the use of statistical methods which provide adjustment for background characteristics.

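### The 8.7.2 sensitivity analyses may impute, drop or carry forward a response for a subject who left for worsening Crohn's disease, while a rescued subject is a fixed failure

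*Protocol*

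**What the plan says.** Section 8.6.1 applies one failure rule to the Week 16 co-primary and the Week 52 key co-secondary endpoints: "Subjects who require the initiation of rescue medication and/or surgery for CD will be considered treatment failures from the date of the introduction". The rule holds whatever the response data show. Section 4.3.2 agrees: "Subjects receiving rescue medication will be considered treatment failures but should remain in the study".

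Section 4.5 lists another way out. Study drug, the study, or both may be stopped for an adverse event that suggests unacceptable risk, "in the judgment of the investigator, including worsening of the disease under study". No section gives that exit failure status. Section 4.5 asks for End of Treatment assessments and every attempt at an ileocolonoscopy. For subjects who stop drug, "an attempt should be made to have the subject followed for 14 days after last administration of study drug".

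Section 8.7.2 uses Worst Case for the primary and key secondary endpoints: too few diary days, or a missing SES-CD, means non-response. Three sensitivity analyses follow. LOCF uses the last non-missing post-baseline value. Multiple imputation fills in missing values. In observed case, "subjects are excluded from the analysis if the subject has insufficient data to be determined as a responder or non-responder". None of the three refers to the reason for leaving.

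**The concern.** Take two subjects whose disease worsens equally at Week 10. One starts rescue medication on study and is a failure in every analysis. The other is withdrawn for worsening before any rescue starts and has no Week 16 data. Worst Case scores both as non-responders. In the sensitivity analyses the first remains a failure, while the second is handled like someone who moved away.

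These analyses are meant to show whether the result depends on missing data. If they also change how worsening is scored, a disagreement with the primary result has two possible causes, and agreement is harder to interpret. Which subjects are affected depends on whether rescue began before exit, and that may differ by arm.

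**Working it through.** **1. The plan's own figure.** Inputs from 8.2 and 8.6.1: 40% placebo, 55% Rifaximin DR, 240 per arm, 1:1 allocation. The test is two-sided ("versus the alternative HA" of a non-zero difference) at 0.05 per endpoint: "Each null hypothesis of no difference will be rejected if the resulting p-value for the respective statistical test is less than 0.05".

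Power = Φ[(δ√n − 1.960√(2p̄(1−p̄))) / √(pP(1−pP) + pR(1−pR))]
= Φ[(0.15×√240 − 1.960×√(2×0.475×0.525)) / √(0.24 + 0.2475)]
= Φ[(2.324 − 1.384)/0.698] = Φ(1.346) = 0.911.

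For both endpoints, if independent, 0.911² = 0.83. The stated 90% and approximately 80% reproduce, so 40% v 55% is a fair per-endpoint anchor.

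**2. How each rule treats a subject who left for worsening, before rescue, with Week 16 or Week 52 data missing.**

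| Analysis | Rescued on study | Left for worsening |
|---|---|---|
| Worst Case | failure | non-responder |
| Multiple imputation | failure | imputed, possibly as a responder |
| Observed case | failure | excluded |
| LOCF | failure | last post-baseline value |

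LOCF needs care. An exit assessment will often supply a worsened value, and that gives non-response. The gap is mainly endoscopic. Scheduled post-baseline ileocolonoscopies follow only Visits 7 and 16 (Appendix 1). A subject with SES-CD ≤ 2 at Week 16 who leaves for worsening at Week 30 without an exit procedure becomes a Week 52 endoscopic remitter. Before Week 16 there is no scheduled post-baseline SES-CD, and baseline is not carried forward.

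**3. Size, first anchor.** Assume 40% and 55% hold with these subjects counted as non-responders, and that a proportion w of each arm leaves for worsening. Dropping them, or imputing at the rate of the remaining subjects, gives p/(1−w):

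| w placebo, w drug | Placebo | Drug | Difference |
|---|---|---|---|
| 10%, 5% | 0.40/0.90 = 44.4% | 0.55/0.95 = 57.9% | 13.5 |
| 15%, 8% | 0.40/0.85 = 47.1% | 0.55/0.92 = 59.8% | 12.7 |
| 20%, 10% | 0.40/0.80 = 50.0% | 0.55/0.90 = 61.1% | 11.1 |
| 5%, 10% | 0.40/0.95 = 42.1% | 0.55/0.90 = 61.1% | 19.0 |

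The reference is 15 points.

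**4. Size, second anchor.** Assume instead 40% and 55% in completers, total dropout d, and a share s of leavers leaving for worsening. Imputing everyone at the completer rate, as the text allows, gives 15.0 points throughout. Scoring the worsening leavers as non-responders gives p(1−ds) under multiple imputation:

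| d placebo, d drug | s = 25% | s = 50% | s = 75% |
|---|---|---|---|
| 20%, 20% | 52.25 − 38.0 = 14.25 | 49.5 − 36.0 = 13.5 | 46.75 − 34.0 = 12.75 |
| 25%, 15% | 52.9 − 37.5 = 15.4 | 50.9 − 35.0 = 15.9 | 48.8 − 32.5 = 16.3 |
| 15%, 25% | 51.6 − 38.5 = 13.1 | 48.1 − 37.0 = 11.1 | 44.7 − 35.5 = 9.2 |

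Worst Case, p(1−d), is the same with or without the change: 44.0 − 32.0 = 12.0, 46.75 − 30.0 = 16.75 and 41.25 − 34.0 = 7.25 points for the three rows.

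**The case against.** The strongest reply is that this is SAP detail. Section 8.0 defers algorithms and data-handling conventions to a SAP that is not shown, and no imputation model is given. Observed case already carries its own warning about interpretation, and the main analyses are unaffected. That limits the weight of the point. It does not remove it, because the protocol itself fixes the failure rule and the three analyses, and states them without exception by reason for leaving.

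A second reply is that worsening is not failure. This stands: no section defines it so, and worsening at Week 10 does not settle either co-primary endpoint, least of all a 3-point SES-CD decrease. Scoring these exits as non-response is a choice. It matches how the protocol scores rescue and how Worst Case scores the same subjects.

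A reader might infer three stronger claims that the protocol does not support:

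- **That treatment started more than 14 days after stopping is never recorded.** For adverse-event discontinuations 4.5 extends follow-up until the condition resolves or stabilises, and 7.5 requires the same for all adverse events. Recording of drugs after the End of Study visit is not spelled out, but a flat 14-day limit is not what the text says.
- **That no reason could be derived.** Section 4.5 requires a reason on the CRF for every withdrawal, listed or not, and 8.4 summarises disposition by reason. Section 7.1.1 does narrow disease exacerbation as an adverse event ("then 'exacerbation' refers to an unexpected worsening from the condition at baseline"), but it also admits worsening symptoms.
- **That a drug excess of adverse-event discontinuations would be hidden.** Section 8.6.5 summarises events by MedDRA preferred term, so Crohn's worsening can be separated.

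**Conclusion.** The point holds for the sensitivity analyses only. As written, they can reclassify subjects who left for recorded worsening as responders, or leave them out, while rescued subjects stay failures. Multiple imputation and observed case are affected directly. LOCF is affected where the last value predates the worsening.

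On the first anchor the Week 16 difference moves from 15 to between about 11 and 19 points. It shrinks in the three scenarios where placebo loses about twice as many subjects to worsening, and grows where the drug loses more. On the second anchor, scoring worsening as non-response moves the multiple-imputation difference from 15.0 to between about 9 and 16 points. All withdrawal rates are assumptions, since 8.2 gives only an overall 20% factor and the scenario with 20% on placebo attributes all of it to worsening. An imputation model using earlier diary data would shift results less. No placebo rate is given for Week 52, so no figure is offered there.

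A reader might infer that the co-primary or key secondary conclusion is at risk. It is not: Worst Case already scores these subjects as non-responders when data are missing. This is a change that should be made, not one on which the trial's main result depends.

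**What to change.** In 8.7.2, add that subjects whose recorded reason for discontinuation is worsening of Crohn's disease or lack of efficacy, and whose Week 16 or Week 52 data are missing, are non-responders in the LOCF, multiple imputation and observed-case analyses, as rescued subjects are. Limit imputation, carry-forward and exclusion to data missing for other reasons.

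In 4.5 and on the CRF, record worsening or lack of efficacy as a discontinuation reason distinct from other adverse events, so that the rule can be applied without interpreting event terms.

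The rule is confined to missing data. A subject who stops drug but has observed Week 16 or Week 52 data keeps those data, and 8.6.1 and the Worst Case rule are unchanged. Nothing here affects when a subject may stop treatment or receive rescue. The cost is a short addition to 8.7.2, one reason code and slightly more analysis work.
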